***Chemotherapy regimens associated with sepsis and treatment management***

- Outcomes relating to UKONS data and prescription data routinely collected in hospital databases (e.g. CANISC/Chemocare).

***Integration of OLO (Sight Diagnostics) system***

- Summaries of discussions and collation of integration issues.

***Design of a larger UK-wide trial***

- Draft protocol suitable for funding application process

## **6 Trial design and setting**

ADVANCE is a non-randomised cohort medical device comparator feasibility study to investigate the ability, safety and acceptability of a community-based point-of-care medical device (the OLO (Sight Diagnostics) System) to improve the patient management pathway for chemotherapy-related suspected neutropenic sepsis. The work will be structured into four separate work packages (WP) as described below.

## 6.1 Work Package 1 (WP1): Cohort comparator study

This WP will identify the key components that may make the pilot and future trial safe and accurate for patients and will be led by the Trial Manager (TM) at the CTR, Cardiff University with support from the CI.

### 6.1.1 Cohort selection

A healthcare worker discussion group meeting held at VCC in April 2019 identified three local areas to explore for use of the OLO (Sight Diagnostics) System in the management of cancer patients:

[figure not shown]
1. Acute admissions between 09:00 and 17:00, supported by Acute Nurse Practitioners and/or Acute Oncology Staff (AOS)
2. Acute admissions out of hours and weekend, supported by Senior Hours Officers (SHOs) and the nursing team
3. Pre-chemotherapy checks of patients who have presented with 'borderline' neutropenic (WBC counts) prior to or on the day of chemotherapy, supported by Phlebotomists.

The staff groups managing these areas vary dependent on whether the patient presents as an acute admission during normal working hours or out of hours and weekend. Similarly, the location of processing of whole blood samples collected during this process, and the gold standard equipment varies dependent on if the patient presents at clinic during or outside of routine local clinic and sample analysis hours. Routine samples collected from patients between 09:00 and 16:00 Monday to Friday will be analysed locally at the VCC Laboratory. Routine samples collected outside of these hours during the evening and/or weekend will be transported to the Cardiff & Vale Health Board Laboratory Service at a separate location (Heath Hospital site, Cardiff) for testing.

Taking these local aspects into account, the discussion group concluded that areas 2 and 3 were most likely to be deliverable locally with maximum impact due to limited availability of some staff groups and logistics of moving device equipment between different locations and teams. Therefore, this feasibility study will investigate two patient cohorts:

**Cohort 1: Suspected neutropenic sepsis:** Patients who, following UKONS assessment via telephone triage have been asked to attend the clinic for further assessment for suspected neutropenic sepsis, and present as an acute admission out of hours and at weekends (Figure 5)

**Figure 5.** Routine patient management pathway for suspected neutropenic sepsis in patients receiving chemotherapy

**Cohort 2:** ‘Borderline’ neutropenia: patients with an inconclusive ‘borderline’ neutrophil count at their pre-chemotherapy assessment who require a repeat test prior to receiving chemotherapy on the planned day of chemotherapy (Figure 6.).

Participants in both cohorts will be asked to consent to the provision of a new study blood sample collected via a CE marked finger prick medical device for analysis using the OLO (Sight Diagnostics) System. The results of the OLO (Sight Diagnostics) System will not be used to manage patients participating in either cohort.

**Cohort 3:** Patients attending Velindre Cancer Centre who are currently or have previously been receiving therapy that might cause a low white blood cell count or neutropenic sepsis. These patients will be asked to participate in the survey part of the study only.

#### **6.1.2 Investigational device**

Sight Diagnostics will supply two OLO Systems) for the purpose of this trial.

[figure not shown]
#### **6.1.3 Acceptability survey**

Participants in a third cohort (WP1 Cohort 3; n=24) will be given an anonymous survey to complete during their hospital in-patient visit. Participants will be asked to return the completed survey to their healthcare worker prior to leaving the hospital.

### **6.2 Work Package 2 (WP2): Patient/carer acceptability**

This qualitative WP2 will assess the key components that would make this feasibility trial and any future larger trial acceptable to patients. WP2 will be led by the VPLG Coordinator or suitable site staff delegate, with support from the Qualitative Researcher, CI and Trial Manager. This WP will focus on a discussion group looking at acceptability to patients and carers for use of the OLO (Sight Diagnostics) system to manage patients with chemotherapy-related suspected neutropenic sepsis and will be implemented prior to WP1.

**Figure 6.** Routine patient management pathway for patients presenting at pre-chemotherapy or paclociclib assessment with borderline neutropenia

Up to 15 members of the VPLG will be invited to participate in a discussion group meeting. Up to 10-15 patients and/or carers will take part. The interview will be held at the participating site, VCC or suitable alternative at the Cardiff. Participant consent will be collected remotely prior to the interview by the VPLG Coordinator or suitable site staff delegate. The interview will include a digital visual demonstration of the OLO System, including the testing equipment and blood sample collection consumables, implemented by the interviewer. The interviewer will use a list of key discussion topics to explore the views of the group about use of the OLO System to manage chemotherapy-related neutropenic sepsis. Key discussion topics will include but not be limited to:

- Views about the current patient management pathway (for example telephone triage, hospitalisation, administration of antibiotics prior to test results, etc.).
- Confidence in the OLO technology as an alternative to the standard test.
- Perceived benefits and disadvantages of the OLO technology.
- Views about the positioning of the OLO technology (for example, community, primary, secondary or tertiary care, Tenovus mobile unit).
- Views about the self-operation of a modified version of the OLO System or similar alternative device.
- Exclusion criteria for future large-scale study (if appropriate) based upon ability to use the equipment effectively, including dexterity and cognitive ability.
- Participant acceptance survey topics.

The discussion group meeting will be manually recorded in anonymised written note format and summarised in anonymised digital format (for example Microsoft Word). The summary will be used to assess the acceptability of the device and application to patients and their carers. It will also be used to develop a participant acceptability survey that, following approval by REC, will be used as a patient evaluation tool to assess acceptability of the equipment. This patient evaluation tool will be completed by participants of WP1, the device cohort comparator study, Cohorts 1-3.

This work will assist in the design of a larger trial and will involve liaison with:

- VPLG.
- Wales Cancer Research Centre (WCRC).
- Tenovus.
- Healthcare workers.

### **6.3 Work Package 3 (WP3): Healthcare worker acceptability**

This qualitative WP3 will assess the key components that would make this trial acceptable to healthcare workers. WP3 will be led by the Trial Manager, with support from a Qualitative Researcher. The WP will focus on a discussion group looking at acceptability to healthcare workers for use of the OLO System to manage patients with chemotherapy-related suspected neutropenic sepsis. The WP will be implemented as soon as possible during, or preferably, after the completion of WP1.

Staff at the WP1 participating site (VCC), Velindre University NHS Trust who are involved in the patient management, antibiotic treatment and sample testing pathway of patients with chemotherapy-related suspected neutropenic sepsis will be invited to participate in a discussion group interview. Up to 20 health care workers will be approached, with approximately 10-15 taking part. The interview will be held in remote digital format. Written informed consent will be collected remotely via email prior to the interview by the interviewee.

The interview will include a remote digital demonstration of the OLO System, including the testing equipment and blood sample collection device consumables delivered by the interviewer. The interviewer will use a list of key discussion topics to explore the views of the group about use of the OLO (Sight Diagnostics) system to manage chemotherapy-related neutropenic sepsis. Key discussion topics will include those detailed above plus:

- Ease of use of the OLO (Sight System (e.g. difficulties, device error rate, difficulties with implementation, and difficulties with interpreting instructions for use).
- Impact on timescales of patient management pathway.
- Preferable blood collection method (venous versus finger prick).
- Preferable location for the analyser within the hospital for different patient cohorts, e.g. laboratory vs clinic, in front or away from patient?
- Perceived benefits to patient and NHS.
- Other points of use in the patient management pathway, e.g. routine use at each regular pre-chemotherapy check during entire chemotherapy course for very susceptible patients?
- Lessons learned from the feasibility study that might impact on the design of a future larger study.
- Other non-cancer potential applications for the OLO System.

The discussion group meeting will be manually recorded in anonymised written note format and summarised in anonymised digital format (for example Microsoft Word). The summary will be used to assess the acceptability of the device and application to healthcare workers.

#### **6.4 Work Package 4 (WP4): Overall benefit to patients, feasibility of integration and economic impact.**

WP4 will assess the overall benefit to patients, feasibility of integration and economic impact of using the OLO System to manage patients with chemotherapy-related suspected neutropenic sepsis and will be implemented after the completion of WP1-3. The WP4 will be led by Planning and Performance Director and Innovations lead at Velindre University NHS Trust, with support from Velindre University NHS Trust management, industry (Sight Diagnostics), NHS Wales technology evaluation and Health economics (Swansea Centre for Health Economics, Swansea University) and the Welsh Government where applicable.

WP4 will identify the key areas relevant for implementation of the OLO System into clinical care, including evaluation within the context of a future larger national trial design. An options appraisal will be developed to optimise the strategy for taking a future larger trial forward. This will include economic, feasibility, and safety components with a view to a future funding bid. We will explore the framework required to adequately inform the potential integration of the investigational device and triage questions into routine practice, within Wales and beyond.

The group will use information from the above in collaboration with patient representatives to design a larger national UK trial suitable for funding via National Institute for Health Research (NIHR) Health Technology Assessment (HTA), the Medical Research Council or other third sector in collaboration with industry to formally assess the OLO System for routine use within the NHS. The aim is to assess cost effectiveness, including issues around hospital care/treatment and admissions. This will be achieved as a collaboration between patients, third sector, industry, clinical staff and the NHS and will involve liaison with:

- NHS Wales.
- Welsh Government.
- NICE.
- UKONS.
- The general public and other appropriate bodies.

## 6.5 Risk assessment

A trial risk assessment has been completed to identify the potential hazards associated with the trial and to assess the likelihood of those hazards occurring and resulting in harm [16]. This risk assessment has been completed using a risk-adapted approach and includes:

- The known and potential risks and benefits to human subjects in relation to the device comparator study.
- All other risks related to the design and methods of the trial (including risks to participant safety, rights and wellbeing, as well as data integrity).
- How high the risk is, compared to standard practice.
- How the risk will be minimised/managed.
- COVID pandemic related risks and mitigations.

The ADVANCE trial intervention comprises an *in vitro diagnostic* (IVD) (OLO System) used in isolation following routine venous blood collection, or in conjunction with a finger prick lancet medical device (HTL-Strefa S.A. Prolance Max Flow Lancet (Lancet) or suitable locally or externally sourced routine alternative) to collect a new study finger prick blood sample. All devices are CE marked for use in the UK and will be used for the intended purpose of the respective CE mark. Therefore, the trial has been categorised as a low risk non-CTIMP study, where the level of risk is no higher than the risk of standard medical care. A copy of the trial risk assessment may be requested from the Trial Manager as part of the local regulatory review process. The trial risk assessment is used to determine the intensity and focus of monitoring activity (see section 25.1).

## 7 Site and Investigator selection

This trial will be carried out at a single participating site (VCC) in Cardiff, Wales, UK. . A Principal Investigator will be assigned at site. The following documents must be in place and copies sent to the ADVANCE trial email account (see contact details on page 4) by the local VCC site team before the site can open to recruitment:

- Investigator Site File (ISF) initially supplied to site by the CTR.
- Favourable opinion of host care organisation/PI from REC.
- A signed delegation of duties document between the Sponsor/Site and CTR.

- Current Curriculum Vitae and GCP training certificate of the PI.
- Completed Site Staff Delegation Log [17] .
- Roles and Responsibilities document [18].
- A training log to evidence suitable training of staff delegated specific responsibilities on the Site Staff Delegation Log (for example, consent training for Senior House Officer (SHOs) responsible for recruiting and consenting participants to WP1).
- Full contact details for all host care organisation personnel involved, indicating preferred contact.
- A copy of the most recent approved version of the Participant Information Sheets and Consent Forms on host care organisation headed paper.
- A copy of the most recent approved GP letter on host care organisation headed paper.
- A set of laboratory normal ranges and laboratory certification/accreditation from the host care organisation laboratory being used for analyses.
- Returned copy of the ADVANCE Self-Evident Correction Log [19] signed by the PI.

Upon receipt of all the above documents, the Trial Manager will send written confirmation to the Principal Investigator/lead Research Nurse detailing that the centre is now ready to recruit participants into the trial. This letter/email must be filed in each site's Site File. Along with the written confirmation, the site should receive the OLO System and consumables and a trial pack holding all the documents required to recruit into the Trial.

Occasionally during the trial, amendments may be made to the trial documentation listed above. The CTR will issue the site with the latest version of the documents as soon as they become available. It is the responsibility of the CTR to ensure that the site obtains local R&D approval for the new documents.

Site initiation will be by attendance at a site initiation meeting, or by teleconference if attendance of key personnel is unfeasible.

## 8 Participant selection

Participants are eligible for the trial if they meet all of the following inclusion criteria and none of the exclusion criteria apply. All queries about participant eligibility should be directed to the Trial Manager before issue of relevant PIS/ ICF and registration and collection of consent.

### 8.1 Inclusion criteria

#### 8.1.1 WP1: Cohort comparator study

##### **Cohort 1: Suspected neutropenic sepsis**

- 1) 18 years old or over
- 2) Received cytotoxic chemotherapy or radiotherapy within the last 6 weeks and has signs and symptoms of neutropenic sepsis or infection and/or a temperature > 38°C or < 36°C
- 3) Admitted to any inpatient area at VCC for assessment for suspected neutropenic sepsis

##### **Cohort 2: Pre-SACT (Systemic anti-cancer therapy) ie borderline neutropenia or palbociclib**

- 1) 18 years old or over
- 2) Patients requiring up to date white cell differential or platelet count immediately prior to therapy i.e: Borderline neutropenia confirmed via a routine pre-chemotherapy whole blood neutrophil count, and require a repeat test either on the day of, or before, the next planned chemotherapy appointment or palbociclib therapy

##### **Cohort 3: Patients who have not had blood assessed by the OLO device but have received therapy that can cause a low white blood cell count.**

- 1) 18 years old or over
- 2) Patients receiving or who have received cytotoxic chemotherapy or radiotherapy

#### 8.1.2 WP2: Patient/Carer focus group interview

- 1) A member of the VPLG who is a current, or previous, cancer patient or carer of a cancer patient
- 2) 18 years old or over

### **8.1.3 WP3: Healthcare worker focus group interview**

- 1) 18 years old or over
- 2) Healthcare worker involved in the management pathway for neutropenic sepsis in cancer patients and/or medical device testing and/or implementation of new medical device at VCC and/or Velindre University NHS Trust

## **8.2 Exclusion criteria**

### **8.2.1 WP1: Cohort comparator study**

#### **Cohort 1: Suspected neutropenic sepsis**

- 1) Has leukaemia or CML.
- 2) Considered by their healthcare professional to be incapable of giving informed consent for any reason (for example senior review has identified severe sepsis).

#### **Cohort 2: 'Borderline' neutropenia**

- 1) Has leukaemia or CML.
- 2) Considered by their healthcare professional to be incapable of giving informed consent for any reason (for example senior review has identified severe sepsis).

N.B. Patients will not be excluded from either cohort if they are:

- Pregnant, lactating or breast feeding
- Have been vaccinated recently
- Have had neutropenic sepsis before

#### **Cohort 3: Survey only cohort**

- 1) Has leukaemia or CML.
- 1) Considered by their healthcare professional to be incapable of giving informed consent for any reason (for example senior review has identified severe sepsis).

### **8.2.2 WP2: Patient/Carer focus group interview**

- 1) Considered by VPLG Co-ordinator to be incapable of giving informed consent for any reason.

### **8.2.3 WP3: Healthcare worker focus group interview**

- 1) Considered by local PI to be incapable of giving informed consent for any reason.

## **9 Recruitment, Screening and registration**

### **9.1 Participant identification**

#### **9.1.1 WP1: Cohort comparator study**

We will approach and recruit a total of 90, 72 and 24 patients respectively to Cohorts 1, 2 and 3 as described in Section 14.1 Sample Size to take part in a non- randomised cohort medical device comparator feasibility study to clinically evaluate the safety and accuracy of using the OLO Sight System to manage chemotherapy-related suspected neutropenic sepsis.

The recruiting healthcare worker will screen the potential participant to ensure that they meet the WP1 eligibility criteria specified in Section 8.4 Inclusion criteria and 8.5 Exclusion criteria of the protocol, before obtaining the participant's consent. Participants will not be approach or registered into the study until the following routine assessments have been initiated for each cohort:

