## 2 Synopsis

Short title	A point of care feasibility study to improve critical care pathways for chemotherapy-related sepsis.
Acronym	ADVANCE
Development phase	Feasibility
CTR Portfolio Number:	746
IRAS Number:	252236
ISRCTN:	TBA
Funder and reference	Tenovus - TIG2017-13
Funder and reference	Velindre Charitable Funds - 2018/18
Funder and reference	Sight Diagnostics UK
Trial design	Non-randomised cohort medical device feasibility study
Population	Cancer patients who present with suspected neutropenic sepsis whilst receiving chemotherapy
Investigational device	OLO-U1 System () (Sight Diagnostics UK Ltd).
Comparator device	Local high throughput lab-based device used to analyse 5 part white cell count
Trial participants	
WP1 Cohort 1: Cancer patients who present with suspected neutropenic sepsis whilst receiving chemotherapy
 
WP1 Cohort 2: Cancer patients who require repeat Full blood count prior to SACT (systemic anti-cancer therapy) ie presented with borderline neutropenia at pre-chemotherapy assessment and require re-testing the day before, or on day of, planned chemotherapy, or will be receiving palbociclib (Ibrance) therapy.
 
WP1 Cohort 3: Cancer patients receiving or who have received cytotoxic chemotherapy or radiotherapy
 
WP2: Cancer patients and carers of cancer patients
 
WP3: Healthcare workers

Planned sample size	
WP1 Total: Approach 90, recruit 72, 65 valid test results.
 
WP1 Cohort 1: Approach 60, recruit 48, 43 valid test results.
 
WP2 Cohort 2: Approach 30, recruit 24, 22 valid test results.
 
WP3 Cohort 3: Approach 24, 19 completed and returned surveys.
 
WP2 : Approach up to 20. Recruit up to 10-15 participants.
 
WP3: Approach up to 20. Recruit up to 10-15 participants.

Planned number of sites	One – Velindre Cancer Centre (VCC), Cardiff, Wales
Inclusion criteria	
WP1 Cohort 1:
 
 
1) 18 years old or over
 
2) Received cytotoxic chemotherapy or radiotherapy within the last 6 weeks and has signs and symptoms or infection and/or a temperature > 38°C or < 36°C
 
3) Admitted to any inpatient area at VCC for assessment for suspected neutropenic sepsis
 

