## **9.3 Recruitment rates**

### **9.3.1 WP1: Cohort comparator study**

60 patients will be approached and 48 participants recruited to Cohort 1: suspected neutropenic sepsis, and 30 patients will be approached and 24 participants recruited to Cohort 2: 'borderline' neutropenic sepsis; giving a total number of 90 patients approached and 72 participants recruited to the device comparator study at a single site over a recruitment period of approximately 3-6 months, i.e. an expected recruitment rate of approximately 12-24 participants per month in total. 24 patients will be approached to participate in Cohort 3: Survey only; with a view to obtaining a minimum of 19 completed and returned surveys.

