##### **Cohort 1 Suspected neutropenic sepsis:**

60 patients will be approached over a three-month period to participate in Cohort 1. If 80% of those approached are recruited (are eligible and provide consent), 48 patients will provide a 95% confidence interval of 68.2% to 88.2%. The widest the 95% confidence interval would be, with an estimated proportion of 50%, 37.7% to 62.3%.

If a valid OLO neutrophil test result is obtained from 90% of recruited patients, 43 patients will provide a 95% confidence interval of 77.8% to 95.5%. If a survey is completed and returned by 80% of recruited patients, 38 patients will provide a 95% confidence interval of 65.7% to 88.3%. In both instances, the widest the 95% confidence interval would be, with an estimated proportion of 50%, 36.4% to 63.6%.

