## **15 Analysis**

### **15.1 Quantitative analysis of WP1 device cohort evaluation**

All quantitative analysis will be documented in the SAP [36] prior to implementation of the analysis.

As this is a feasibility study, statistical analysis of study outcomes will be descriptive in nature. Continuous data will be reported as means and standard deviations, or medians and interquartile ranges, as appropriate. Categorical data will be reported as frequencies and proportions. Outcomes will be estimated with their associated 95% confidence intervals.

No formal hypothesis testing will take place.

While subsequent funding is not formally linked to satisfying any specific progression criteria, we propose the following as indicators that a larger study is feasible (NB. Failure to meet one or more of the criteria would indicate that modifications are required, with potentially further feasibility testing, prior to a larger study) as described in Table 7.

**Table 7.** Trial progression criteria

Outcome	Criteria
Recruitment	At least 80% of patients approached to take part provide consent
Intervention adherence	At least 90% of recruited participants receive the OLO test
Intervention fidelity	A valid test result is obtained from at least 90% of recruited participants who receive the OLO test
Survey fidelity	A survey is completed and returned from at least 80% of recruited participants who are given the survey
Data collection	At least 80% of recruited participants have clinical outcome data available for statistical analysis
Staff focus groups	Focus group data indicates that the OLO test is acceptable
Patient focus groups	Focus group data indicates that the OLO test is acceptable

There will be no interim analyses other than TMG review of WP1 SAE's at TMG meetings, Trial Manager review of screening logs through the WP1-3 recruitment phases, and Trial Manager review of data entry after approximately half of the participants have been recruited to WP1.

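### Section 9.1.1 gives the combined totals for Cohorts 1 and 2 as per-cohort recruitment targets, and Table 7 uses a different denominator for valid results from the rest of the protocol

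*Protocol*

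**What the plan says.** On the recruitment targets:

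- Section 9.1.1: "We will approach and recruit a total of 90, 72 and 24 patients respectively to Cohorts 1, 2 and 3". The sentence refers to Section 14.1 for the basis and gives one number per cohort for both approaching and recruiting.
- Section 14.1.1, Cohort 1: "60 patients will be approached over a three-month period to participate in Cohort 1", with 48 recruited at an assumed 80%. Cohort 2 has 30 approached and 24 recruited. Cohort 3 has 24 approached and 19 returned surveys.
- Section 9.3.1: "60 patients will be approached and 48 participants recruited to Cohort 1". It gives 30 and 24 for Cohort 2, adds the two cohorts to 90 approached and 72 recruited, and seeks at least 19 surveys from 24 patients in Cohort 3.
- Synopsis: "WP1 Total: Approach 90, recruit 72, 65 valid test results", followed by the same per-cohort figures. The lines for Cohorts 2 and 3 carry the labels WP2 and WP3, but the numbers are those of section 14.1.1.

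On valid results:

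- Section 5.3 defines the proportion with a valid result out of all recruited participants.
- Section 14.1.1 plans on that basis: "If a valid OLO neutrophil test result is obtained from 90% of recruited patients, 43 patients" in Cohort 1, and 22 of 24 in Cohort 2.
- Table 7 in section 15.1 splits this into two criteria. One is adherence: "At least 90% of recruited participants receive the OLO test". The other is fidelity: at least 90% valid among the recruited participants who receive the test.

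**The concern.** Section 9.1.1 is the operational text on whom to approach and recruit, and its numbers contradict the section it cites. Anyone working from it alone would aim for far more patients in Cohorts 1 and 2 than the sample size section justifies. They would also have no separate figures for approached and recruited patients, although the 80% recruitment criterion in Table 7 needs both.

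The denominator matters because the valid-result proportion is both a secondary feasibility outcome and an indicator for a larger study. With two denominators, the same data can meet the Table 7 criteria and still fall clearly below the proportion on which section 14.1.1 bases its precision.

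**Working it through.** **1. Reproducing the plan's own figures.** Counts are the approached or recruited number times the assumed rate, rounded to the nearest whole number:

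- Recruited: 0.80 × 60 = 48; 0.80 × 30 = 24.
- Surveys in Cohort 3: 0.80 × 24 = 19.2, so 19.
- Valid results: 0.90 × 48 = 43.2, so 43; 0.90 × 24 = 21.6, so 22.

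The 95% intervals are Wilson score intervals, (p + z²/2n ± z√[p(1−p)/n + z²/4n²]) / (1 + z²/n) with z = 1.96:

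- 48/60: 68.2% to 88.2%
- 43/48: 77.8% to 95.5%
- 24/30: 62.7% to 90.5%
- 22/24: 74.2% to 97.7%
- 19/24: 59.5% to 90.8%

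All match section 14.1.1, so its per-cohort numbers are internally sound.

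**2. Where 90 and 72 come from.** Approached: 60 + 30 = 90. Recruited: 48 + 24 = 72. Section 9.1.1 assigns the first sum to Cohort 1 and the second to Cohort 2. Its 24 for Cohort 3 is the correct number to approach, but not the number of surveys expected (19).

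**3. Size of the discrepancy if read literally.**

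- Cohort 1 recruited: 90 against 48, a ratio of 90/48 = 1.9. Approached: 90/60 = 1.5.
- Cohort 2 recruited: 72 against 24, a ratio of 72/24 = 3.0. Approached: 72/30 = 2.4.
- Cohorts 1 and 2 recruited: 90 + 72 = 162 against 72, a ratio of 2.25.

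**4. Which version the rest of the protocol supports.** Section 9.3.1 expects 12 to 24 recruits per month over 3 to 6 months. This fits a total of 72 (72/6 = 12; 72/3 = 24). A total of 162 would need 162/6 = 27 to 162/3 = 54 per month. The local audit in section 4.2.1 found 96 suspected cases admitted in three months. Recruiting 90 to Cohort 1 in the three months of section 14.1.1 would take 90/96 = 94% of that number, although section 6.1.1 describes Cohort 1 as out-of-hours and weekend admissions.

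**5. The valid-result denominator.**

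- Planned, out of all recruited: 43 + 22 = 65, and 65/72 = 90.3%.
- Table 7 adherence minimum: 0.90 × 72 = 64.8, so 65 tested.
- Table 7 fidelity minimum among those 65: 0.90 × 65 = 58.5, so 59 valid (59/65 = 90.8%; 58/65 = 89.2% would miss).
- Out of all recruited: 59/72 = 81.9%.

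Testing more participants raises the minimum (66 tested needs 60 valid), so 59 is the lowest count that meets both criteria. The gap from the plan is 65 − 59 = 6 participants, or 6/72 = 8.3 percentage points. The number 65 appears twice by coincidence: as planned valid results and as the minimum tested.

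**The case against.** The section 9.1.1 sentence is plainly a transcription slip. It sends the reader to Section 14.1, and every other statement of the targets is correct, so a site would have to overlook all of them to recruit the wrong numbers. That is fair on likelihood. It does not remove the need to correct a wrong target in the recruitment section.

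On the denominator, Table 7 sets floors and forecasts nothing. Planning for 90% valid among all recruited is compatible with a rule that would tolerate less. Section 14.1 never mentions Table 7 and presents its counts only to show interval width. This stands: the stated precision is not wrong. What remains is that one quantity is judged on two denominators.

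Two stronger readings are tempting and are not supported:

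- *The planned counts fail the Table 7 thresholds.* Some single-cohort counts do fall just short: 43/48 = 89.6% against 90%, and 38/48 and 19/24 (both 79.2%) against 80% for surveys. Each is short by one participant through rounding down. Nothing says the counts were meant to satisfy Table 7, and Table 7 is not stated to apply by cohort. Combined valid results (65/72 = 90.3%) and recruitment (72/90 = 80.0%) meet their criteria.
- *A trial running exactly to plan would almost always fail some criterion.* A joint probability over all numeric criteria needs planning rates for receiving the test and for data availability, and the protocol gives neither. Section 15.1 also describes the criteria as indicators not formally linked to funding.

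**Conclusion.** Section 9.1.1 is wrong as written for Cohorts 1 and 2. It overstates recruitment by a factor of 1.9 and 3.0 respectively, and it merges approached with recruited in all three cohorts. This rests only on comparing the protocol's own statements and needs no outside assumption. It is an error in stating the targets, not evidence that the planned sample size is other than 72 recruited to Cohorts 1 and 2.

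The denominator inconsistency is real but secondary. Both device criteria in Table 7 can be met with 59 of 72 valid results (81.9%), against 65 of 72 (90.3%) planned. This assumes that 72 are recruited and that Table 7 is applied to Cohorts 1 and 2 combined.

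**What to change.** In section 9.1.1, replace the sentence giving the targets with: *approach 60, 30 and 24 patients for Cohorts 1, 2 and 3; recruit 48 and 24 to Cohorts 1 and 2 (90 approached and 72 recruited in total) and obtain 19 completed surveys in Cohort 3.*

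In Table 7, set the valid-result criterion on all recruited participants, to match sections 5.3 and 14.1.1. The minimum is then 0.90 × 72 = 64.8, so 65, which is the planned number.

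The cost is protocol wording. Sample size, data collection and the section 14.1.1 intervals stay as they are. The valid-result criterion becomes stricter (65 instead of as few as 59). Once it is met, the adherence criterion is met too, because a participant must be tested to have a valid result. The adherence line can stay to show whether a shortfall comes from untested participants or from invalid results.
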